#### 2.4.3.2 Compliance

Compliance will be assessed using the following parameters:

- The mean injection frequency of OLE IMP will be defined for each patient as the average number of days between 2 consecutive injections, that is: (last injection date first injection date)/(number of injections -1) for patients receiving at least 2 injections.
- The overall compliance for injections will be defined for each patient as: 100-(%days with under-planned dosing + %days with above-planned dosing). Under-planned and above-planned dosing will be defined as follows, considering that injections should be performed every 2 weeks (±3 days as per protocol):
  - the %days with under-planned dosing will be defined for each patient as the number of days with no injection administered within the previous 17 days divided by the duration of IMP injection exposure in days. For example if a patient takes a dose 18

25-Jan-2016 Version number: 1

days after his/her previous injection, then 1 day is counted as a day under-planned dosing.

- the %days with above-planned dosing will be defined for each patient as the number of days with more than one injection administered within the 11 days before divided by the duration of IMP injection exposure in days. For example if a patient takes a dose 9 days after his/her previous injection, then 2 days are counted as days above-planned dosing.

These parameters will be summarized descriptively (N, Mean, SD, Median, Minimum and Maximum).

The percentage of patients whose overall compliance for injections is <80% will be also summarized as well as numbers and percentages of patients with 0%, >0% and  $\leq$ 5%, >5% and  $\leq$ 10%, >10% and  $\leq$ 20%, and >20% days with above-planned dosing and numbers and percentages of patients with 0%, >0% and  $\leq$ 5%, >5% and  $\leq$ 10%, >10% and  $\leq$ 20%, and >20% days with underplanned dosing.

The overall compliance (quantitatively and by category (<80% vs  $\ge80\%$ )) will be also summarized by the following time periods:  $\ge0$  and  $<26, \ge26$  and  $<52, \ge52$  and  $<78, \ge78$  and  $<104, \ge104$  and  $<130, \ge130$  and <156, and  $\ge156$  weeks.

According to protocol, cases of overdose are reported in the AE e-CRF pages and will be described in the AE analysis (see Section 2.4.5.1 and Section 2.1.4.1).

#### 2.4.4 Analyses of efficacy endpoints

Efficacy analyses will be presented overall as well as separately according to treatment received in the parent study (placebo versus alirocumab (regardless of dose)) unless otherwise specified.

#### 2.4.4.1 Analysis of primary efficacy endpoint(s)

Not Applicable

#### 2.4.4.2 Analyses of secondary efficacy endpoints

No formal statistical comparisons will be performed for efficacy variables.

Central laboratory values (in conventional (US) and international units), percent changes from baseline of the parent study, and/or when appropriate absolute change from baseline of the parent study (in conventional (US) and international units), for calculated LDL-C, Total-C, HDL-C, fasting TG, non-HDL-C, Apo B, Apo A-1, ratio Apo B/Apo A-1(only absolute changes) and Lp (a) at time points when these lipid parameters are to be collected as per protocol will be summarized over time in the mITT population as described below.

25-Jan-2016 Version number: 1

Quantitative descriptive summaries (number of available data, mean, SD, median, minimum and maximum) by planned time point will be presented for all lipids using observed (i.e. non-missing) data. Missing data will not be imputed. In addition, standard error (SE) and the 95% confidence interval (CI) for the mean will be provided for lipids other than TGs and Lp(a) and Q1 and Q3 will be provided for TGs and Lp(a).

The time profile in percent change from baseline of each parameter (except ratio ApoB/Apo A-1 where absolute change will be used) will be plotted according to treatment received in the parent study by using mean and SE except for TGs and Lp(a). For these 2 parameters, median, Q1 and Q3 will be plotted.

In addition, binary variables for LDL-C will be also described by planned time point by presenting number and percentage of patients reaching the target.

In order to analyze the effect of forced down-titration from 150 mg Q2W at the end of the parent study to 75 mg Q2W at the entry in OLE, analyses of percent change in calculated LDL-C, ApoB, non-HDL-C, TGs and Lp(a) from Week 78 of parent study (alirocumab 150 mg) to Week 8 of OLE study (alirocumab 75 mg) will be quantitatively summarized on the 2 following categories of patients:

- patients of the mITT population who were up-titrated in EFC12492 (FH1) and R727-CL-1112 (FH2) parent studies (patients had to be up-titrated in a blinded manner, using an automated process when LDL-C at Week 8 was ≥70mg/dL)
- patients of the mITT population coming from LTS11717 who all received alirocumab 150 mg Q2W throughout the parent study.

The gain efficacy due to up-titration from 75 mg Q2W to 150 mg Q2W in the parent study will be informally compared to the loss of efficacy due to forced down-titration to 75 mg Q2W at the entry in OLE in patients of the mITT population who were up-titrated in FH1 and FH2 studies. The percent change in calculated LDL-C from Week 12 (alirocumab 75 mg) to Week 24 (alirocumab 150 mg) in parent study and the percent change in calculated LDL-C from Week 78 in parent study (alirocumab 150 mg) to Week 8 in OLE study (alirocumab 75 mg) will be quantitatively summarized (number of available data, mean, SD, median, minimum, maximum, Q1 and Q3).

The effect of alirocumab 75 mg Q2W dose will be informally compared to the effect of alirocumab 150 mg Q2W dose in patients of the mITT population coming from LTS11717 who all received alirocumab 150 mg Q2W in the parent study. The percent change in calculated LDL-C from baseline of the parent study to Week 8 (alirocumab 150 mg) in parent study and the percent change in calculated LDL-C from Day1 in OLE study (after a washout period of 10 weeks) to Week 8 in OLE study (alirocumab 75 mg) will be quantitatively summarized. Same analysis will be done for ApoB, non-HDL-C, Lp(a) and TGs.

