Although the background therapies, statin at MTD or other LMT (if applicable), should be maintained stable if possible, they might be adjusted based on Investigator judgment, in particular in case of tolerability issue. The reasons of any adjustment should be documented and recorded in the e-CRF.

For adjustments based on LDL-C values, simultaneous adjustments in alirocumab dose and any LMT should be avoided.

Patients will be asked to continue to follow a stable diet (equivalent to the National Cholesterol Education Program Adult Treatment Panel III Therapeutic Lifestyle Changes (NCEP ATP III TLC) during the study.

Patients will return for regular on site visits according to the flow chart for additional laboratory testing, questionnaires, clinical examination and IMP dispensation.

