# 2.3.1 Efficacy population

The efficacy population considered for efficacy analyses will be the mITT population.

The mITT population is defined as all patients who took at least one dose or part of a dose of the open-label IMP injection and with both of the following conditions met:

- Availability of a baseline (from parent study) calculated LDL-C
- Availability of at least one calculated LDL-C during the efficacy treatment period in one of the analysis windows from Week 8 onwards.

The efficacy treatment period is defined as the time period from the first open-label IMP injection up to the day of last injection +21 days.

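### The comparison of up-titration gain with down-titration loss sets side by side two percent changes with different denominators, so a fully reversed effect reads as a loss larger than the gain

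*SAP*

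**What the plan says.** SAP 2.4.4.2 states the aim: "The gain efficacy due to up-titration from 75 mg Q2W to 150 mg Q2W in the parent study will be informally compared" and, for the other half, it "will be informally compared to the loss of efficacy due to forced down-titration to 75 mg Q2W at the entry in OLE". The patients are those in the mITT population who were up-titrated in FH I and FH II.

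Two measures are named:

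- Gain: "The percent change in calculated LDL-C from Week 12 (alirocumab 75 mg) to Week 24 (alirocumab 150 mg) in parent study".
- Loss: "the percent change in calculated LDL-C from Week 78 in parent study (alirocumab 150 mg) to Week 8 in OLE study (alirocumab 75 mg").

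Each is to be summarised by number of available data, mean, SD, median, minimum, maximum, Q1 and Q3. No absolute change, log ratio or common-denominator version is listed for this contrast, and nothing warns that the bases differ.

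Elsewhere in 2.4.4.2 the SAP does plan summaries on a common base, namely "percent changes from baseline of the parent study, and/or when appropriate absolute change from baseline of the parent study". Section 2.4.4 sets how these are shown: "Efficacy analyses will be presented overall as well as separately according to treatment received in the parent study". That layout does not isolate the up-titrated FH I/FH II patients.

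**The concern.** A percent change is read against its starting value. The gain starts from the higher LDL-C (75 mg) and the loss from the lower one (150 mg). The same number of mg/dL is therefore a larger percentage on the way up than on the way down. Each figure is valid alone; the fault lies in comparing their sizes, which is the stated purpose of the analysis.

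A reader would conclude that stepping down cost more than stepping up gave, even if every patient returned exactly to the earlier 75 mg level. Equal percentages, which look like exact reversal, would mean that the reversal was incomplete. With no test or confidence interval planned for the contrast, the scale carries the whole interpretation.

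The two summaries also need not cover the same patients. The LDL-C requirement for mITT, beyond a parent baseline value, is only "Availability of at least one calculated LDL-C during the efficacy treatment period in one of the analysis windows from Week 8 onwards", missing data are not imputed, and each summary reports its own number of available data.

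**Working it through.** **Inputs.** The time points and doses come from SAP 2.4.4.2. The percent-change formula, 100 × (later − start)/start, is given in Protocol 9.2.1 for the parent baseline and is applied here by analogy to the Week 12 and Week 78 starting values. The plan states no figure for this contrast, so there is none to reproduce. LDL-C levels and g are assumed.

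**General form.** Write W12, W24, W78 for the parent-study values and O8 for OLE Week 8.

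- Gain = 100 × (W24 − W12)/W12
- Loss = 100 × (O8 − W78)/W78
- Size ratio, loss to gain = [(O8 − W78)/(W12 − W24)] × (W12/W78)

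The first factor compares the two steps in mg/dL. The second, W12/W78, comes only from the denominators.

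**No drift between Weeks 24 and 78.** Let W12 = L, W24 = W78 = L(1−g), and let a fraction f of the gain reverse, so O8 = L(1−g) + fgL.

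- Gain = −100g
- Loss = +100fg/(1−g)
- Size ratio = f/(1−g), which is 1/(1−g) at full reversal
- Gap in size at full reversal = 100g/(1−g) − 100g = 100g²/(1−g) points
- The percentages are equal in size when f = 1−g

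| g (assumed) | Gain | Loss, full reversal | Gap (points) | Loss shown as larger than gain when f exceeds |
|---|---|---|---|---|
| 10% | −10.0% | +11.1% | 1.1 | 90% |
| 15% | −15.0% | +17.6% | 2.6 | 85% |
| 20% | −20.0% | +25.0% | 5.0 | 80% |
| 25% | −25.0% | +33.3% | 8.3 | 75% |
| 30% | −30.0% | +42.9% | 12.9 | 70% |

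The ordering misleads only for 1−g < f ≤ 1. At g = 20% and half reversal the loss is 100 × 0.5 × 0.20/0.80 = +12.5% against −20.0%, still in the right order.

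**The same data on a common base.** Assume 150 mg/dL at parent baseline, 90 on 75 mg, 72 on 150 mg, and full reversal.

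- SAP measures: 100 × (72−90)/90 = −20.0% and 100 × (90−72)/72 = +25.0%
- Percent of parent baseline: 100 × (72−90)/150 = −12.0 and 100 × (90−72)/150 = +12.0 points

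**Means.** The table describes a single patient, or medians. With log-normal within-patient variation of coefficient of variation c, independent between visits, the expected ratio of two visits is multiplied by 1 + c². At g = 20% and an assumed c of 15%, 1 + c² = 1.0225. The mean gain is 0.80 × 1.0225 − 1 = −18.2% and the mean loss 1.0225/0.80 − 1 = +27.8%, a ratio of 1.53. A simulation gave −18.2% and +27.9%. For means, 1/(1−g) therefore understates the distortion.

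**The case against.** The strongest reply is that the stated inflation need not appear in the data. The factor 1/(1−g) needs full reversal and no drift, whereas the contrast runs from parent Week 12 to OLE Week 8. During the OLE, background lipid therapies should stay stable if possible, but "they might be adjusted based on Investigator judgment, in particular in case of tolerability issue". With g = 20%, shifts of ±10% in the Week 78 or OLE Week 8 level move the loss-to-gain ratio from 0.11 to 2.64, against 1.25 without drift. With values of 100, 80, 88 and 100 the SAP would show −20.0% against +13.6%, and the loss would read as the smaller one. A common scale does not remove drift: the same values give −20 against +12 mg/dL.

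This limits what can be predicted, but the artefact remains. In that example the mg/dL ratio is 12/20 = 0.60, and the denominators still multiply it by 100/88 = 1.14, giving 0.68. Drift adds to the problem and does not cancel it systematically.

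Further points are fair. No figure in the SAP is miscalculated, and each percentage is labelled with its weeks and doses. The size is wholly assumed, and at g = 10% the gap is only 1.1 points. The comparison is explicitly informal. Differences in patient numbers would be visible, and restricting to complete cases loses some patients. These points keep the matter from being critical. They do not show that the two percentages are comparable, and labels alone do not let a reader convert the published means exactly.

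**Conclusion.** The concern holds. As written, the comparison confounds any real difference between gain and loss with a denominator effect of W12/W78, which is 1/(1−g) without drift. Under full reversal the loss is overstated relative to the gain by 1.1 points at g = 10%, 5.0 at 20% and 12.9 at 30%, and by more for means.

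The direction assumes that LDL-C on 150 mg at Week 78 is below LDL-C on 75 mg at Week 12. The sizes rest on assumed g, no drift and full reversal. The consequence is confined to a descriptive comparison that is not among the secondary efficacy endpoints listed in SAP 2.1.3.2, and the primary safety conclusion is unaffected. It should be corrected because the comparison serves no purpose other than the reading that the scale distorts.

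**What to change.** Keep the two planned percent changes on all available data. Beside them, in the up-titrated FH I/FH II patients of the mITT population who have all four LDL-C values, summarise both steps on one scale named in advance. A suitable choice is the difference in percent change from the parent-study baseline: parent Week 24 minus Week 12 for the gain, and OLE Week 8 minus parent Week 78 for the loss. State in the SAP that the gain-versus-loss reading rests on this scale.

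A within-patient sum of the two steps with a 95% CI is optional. With parent baseline B, it equals 100 × [(O8 − W12) − (W78 − W24)]/B. Drift between Weeks 24 and 78 and changes in background therapy therefore also move it, and a note should say that a non-zero sum does not isolate the effect of dose.

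The cost is a short SAP revision and one derived variable for each step. The four LDL-C values and the parent baseline are already used in the plan, so no new data are needed. Some patients drop out of the added display, but the available-data summaries remain beside it.

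### The 75 mg versus 150 mg comparison in LTS11717 patients has no per-patient difference, no interval for that difference and no common patient set

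*SAP*

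**What the plan says.** SAP 2.4.4.2 takes mITT patients from LTS11717 who received 150 mg in the parent study: "The effect of alirocumab 75 mg Q2W dose will be informally compared to the effect of alirocumab 150 mg Q2W dose in patients". The 150 mg effect is "The percent change in calculated LDL-C from baseline of the parent study to Week 8 (alirocumab 150 mg) in parent study". The 75 mg effect is "the percent change in calculated LDL-C from Day1 in OLE study (after a washout period of 10 weeks) to Week 8 in OLE study". Both are to be summarised quantitatively. No list of statistics is given, and the contrast between the two changes is not defined.

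Just before this, the section sets out a similar comparison for patients up-titrated in FH1 and FH2: "The gain efficacy due to up-titration from 75 mg Q2W to 150 mg Q2W in the parent study will be informally compared" with the loss on returning to 75 mg at OLE entry. The gain is the Week 12 to Week 24 change in the parent study. The loss is the change from parent Week 78 to OLE Week 8. The listed statistics stop at n, mean, SD, median, range and quartiles.

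These rules bear on both comparisons:

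- Summaries are made "using observed (i.e. non-missing) data. Missing data will not be imputed" (SAP 2.4.4.2).
- "No formal statistical comparisons will be performed for efficacy variables" (SAP 2.4.4.2).
- Time-point means of lipids other than TG and Lp(a) get a standard error and a 95% CI (SAP 2.4.4.2).
- The mITT population needs a parent-study baseline LDL-C and "Availability of at least one calculated LDL-C during the efficacy treatment period in one of the analysis windows from Week 8 onwards" (SAP 2.3.1).
- LDL-C measured by beta quantification, used when TG exceeds 400 mg/dL, is left out of the calculated LDL-C endpoints (SAP 2.1.3).

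**The concern.** The stated purpose is to compare the effects of two doses, and each patient can supply both effects. The natural quantity is the per-patient difference between the two changes. The plan produces two marginal summaries instead and leaves the reader to subtract one mean from the other.

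This has two consequences. First, the SD of the difference depends on the within-patient correlation, which two marginal SDs do not contain, so the precision of the contrast cannot be worked out from the report. Second, the comparison needs four LDL-C values per patient, and mITT membership guarantees only the parent baseline. A patient can enter one mean and not the other, and part of an apparent dose difference could then reflect who had usable samples.

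This comparison sets each dose's effect, from a starting value off alirocumab, side by side in the same patients. A reader would turn to it for a dose contrast.

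**Working it through.** **Plan's own figure.** There is none. SAP 1.3 states that no sample-size calculation was performed, and no precision is stated for this comparison. What follows is illustration, and its assumptions are marked.

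**Which values mITT membership guarantees**

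| Value needed | Required by SAP 2.3.1? |
|---|---|
| Parent baseline | Yes |
| Parent Week 8 | No |
| OLE Day 1 | No |
| OLE Week 8 | No (any window from Week 8 onwards suffices) |

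With observed data only and no imputation, nothing keeps the two patient sets equal. A visit with TG above 400 mg/dL also loses its LDL-C value for this analysis even when a sample was taken.

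**Marginal summaries do not fix the precision.** Two fixed sets of 200 simulated changes (assumed SD about 20 points) were paired in three ways. The mean difference was 14.7 points each time. The 95% half-width is 1.96 × SD of the difference / √200:

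- same rank order: SD 2.08, half-width 0.3
- random pairing: SD 25.68, half-width 3.6
- reversed order: SD 36.42, half-width 5.1

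The same marginal summaries are therefore compatible with half-widths from 0.3 to 5.1 points.

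**Plausible size of the gain.** Assume n = 200, SD 25 points in each period and correlation r.

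- Read as unpaired: 1.96 × 25 × √(2/200) = 4.9 points.
- Paired: 1.96 × 25 × √(2(1 − r)/200) = 4.9 × √(1 − r), which gives:
  - r = 0.3: 4.1 points (16% narrower)
  - r = 0.5: 3.5 points (29% narrower)
  - r = 0.7: 2.7 points (45% narrower)

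The documents give 385 heFH patients randomised in LTS11717 over both arms (Protocol 4), without the allocation ratio. Assume 50% to 67% were on alirocumab and 70% to 90% of those entered the OLE. Then n runs from 385 × 0.5 × 0.7 ≈ 134 to 385 × 2/3 × 0.9 = 231. With SD 20 to 30 and r 0.2 to 0.7:

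- Narrowest paired half-width: 1.96 × 20 × √(2 × 0.3/231) = 2.0 points.
- Widest paired half-width: 1.96 × 30 × √(2 × 0.8/134) = 6.4 points.
- Unpaired, over the same n and SD: 3.6 to 7.2 points.

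**Non-matching sets.** Suppose each of 231 patients has a 90% chance of a usable change in each period, independently (assumed). Each mean then uses about 208 patients, 231 × 0.81 ≈ 187 have both changes, and 231 × 0.18 ≈ 42 count in one mean only. The shift in a mean is the fraction missing times their response gap. For 5% to 15% missing and a gap of 5 to 20 points (assumed), it runs from 0.05 × 5 = 0.25 to 0.15 × 20 = 3 points. At 10% and 20 points it is 2 points.

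**Why FH1/FH2 needs different handling.** Gain and loss have opposite signs and different denominators. Take a patient who goes from 140 to 100 mg/dL on up-titration and from 100 back to 140 at OLE entry. The changes are −28.6% and +40%. Their difference is 68.6 points and their sum is 11.4 points, yet the patient gained and lost exactly 40 mg/dL. On the absolute scale the sum is −40 + 40 = 0. On the log-ratio scale it is ln(100/140) + ln(140/100) = 0.

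**The case against.** The strongest reply is that the plan calls the comparison informal, rules out formal comparisons, and concerns a secondary objective in a study whose primary objective is safety. That is fair as to weight. It does not dispose of the point, because an interval without a test is still descriptive. Protocol 11.4.3 and SAP 2.4.4.2 themselves give confidence intervals alongside untested percent changes.

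Four further points stand:

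- SAP 2.4.4.2 already plans a paired 150 mg to 75 mg contrast in these LTS11717 patients, the change from parent Week 78 to OLE Week 8. It gives one number per patient and so has one common set.
- Each of the two changes may receive its own CI under the section's general rule, although the text does not say so for this comparison.
- With a positive correlation, reading the two means as unpaired gives too wide an interval, which errs on the cautious side. If the two sets coincide, the mean difference is unaffected.
- A paired interval covers sampling error only. The two periods start more than 18 months apart. Background therapy may be adjusted (Protocol 8.8.1). Parent baseline followed selection on a screening LDL-C threshold, and OLE Day 1 did not. Protocol 9.1 also expects residual drug effect until 10 weeks after stopping, which is when OLE Day 1 falls. These limits remain after the fix.

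**Conclusion.** The point holds as a minor improvement. For the LTS11717 comparison, the SAP defines neither the per-patient contrast between doses, nor an interval for it, nor the patients on whom it rests. How much precision would be gained, and whether unequal sets would shift the result at all, depend on an SD, a correlation and a missing-data pattern that the documents do not give. The figures above show a possible range and predict nothing.

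A reader might infer three stronger things that the documents do not support:

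- That this is the trial's only same-patient comparison of the two doses. The planned Week 78 to OLE Week 8 change is another. SAP 2.4.3.1 also compares low LDL-C counts between the two periods in LTS11717 patients.
- That the plan gives no precision at all. The two changes may each have a CI. The interval that is missing is the one for their difference.
- That the dose contrast will be biased by missing data. The SAP does not prevent unequal sets, but nothing shows that they will occur or matter.

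**What to change.** In SAP 2.4.4.2, for LTS11717:

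- Restrict the comparison to patients with both changes available, and show both marginal changes on that set.
- For calculated LDL-C and non-HDL-C, report the per-patient difference (OLE Day 1 to Week 8 change minus parent baseline to Week 8 change) as n, mean, SD, median, Q1, Q3 and a descriptive 95% CI, with no test.
- For TG, report the median, Q1 and Q3 of the difference.

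Apo B and Lp(a) are not listed because the Protocol schedules neither at OLE Week 8 (flow chart in 1.2; section 10.1.1.3).

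For the FH1/FH2 gain-versus-loss comparison, apply the common set only and do not subtract the two percent changes. If a per-patient contrast is wanted, use a symmetric scale with a stated sign, such as the sum of the two absolute (mg/dL) changes or of the two log-ratio changes, where zero means that the loss equals the gain.

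The cost is a few lines of SAP text and one derived variable, with no new data. The downside is a slightly smaller common set; reporting its n beside the number available for each change makes the loss visible.
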